4.10.2 Interaction test

We will assess whether the effect of NeuroSAFE on IIEF-5 at 12 months and ICIQ at 3 months differs according to pre-operative bilateral nerve sparing recommendation (BNSR), as defined in 3.9.2.

This will be assessed by testing for an interaction between BNSR and treatment arm in the primary and secondary outcome models (linear regression adjusted by site, age and baseline IIEF-5 or ICIQ).

Interaction test p-values will be interpreted in consideration of the low power of the interaction test, the number of subgroups tested, and the biological plausibility of the interaction.

4.10.3 Subgroup analysis within the non-BNSR participants

We will compare outcome between the NeuroSAFE and standard arm, within the subgroup of participants where bilateral nerve sparing was not recommended.

We will estimate the difference in the primary (IIEF-5 at 12 month) and the main secondary (ICIQ at 3 months) outcomes between arms in this subgroup, using the same analysis model specified in section 4.7 and 4.8 (linear regression adjusted for age, site and baseline IIEF-5 or ICIQ) but restricted to participants without BNSR.

We may also report (without formal testing) on the difference in other secondary and descriptive outcomes within this subgroup, if appropriate.

Although this subgroup analysis may be less powered than the primary analysis of the trial, we expect around 2/3 of the trial participants to belong to this subgroup. This sample size should be sufficient power to detect moderate or large difference between arms.

We will not compare the outcomes within the converse subgroup (participants for whom bilateral never sparing was recommended), which would be of lesser relevance and likely to lack statistical power.

4.11 Missing data sensitivity analysis

We will conduct sensitivity analysis under different missing data assumptions for the primary outcome.

4.11.1 Missing at random

If important predictors of missing data are identified, we may report additional results under missing at random assumption, adjusting for these factors in the main regression model (for baseline predictors), or conducting multiple imputation.

4.11.2 Missing not at random

We will also conduct a sensitivity analysis under not-at-random assumption using reference-based multiple imputation (Carpenter, 2013). We will impute the missing data under the 'last-mean-carried-forward' approach, corresponding to assuming the IIEF-5 score would have remained similar to the last score observed before dropping out (akin to the 'Last-Observation-Carried-Forward' approach, but appropriately allowing for other predictors, and variation in the imputed values).

The multiple imputation model will include the outcomes at each time point, the baseline covariates and other important predictors of missing data and will be stratified by arm. We will assume interim missing (missing assessments with later outcome data available) to be missing-at-random. If some participants have no IIEF-data available (at visit 2, 3 and 4), we will assume they had the lowest score at 3 months (1 for IIEF-5) at visit 2, before conducting the imputation.

The analysis model will be the same as the primary analysis model, and the results will be combined using Rubin's rules.

5 References

Avery, K. a. (2004). ICIQ: a brief and robust measure for evaluating the symptoms and impact of urinary incontinence. *Neurourology and Urodynamics: Official Journal of the International Continence Society*, 322--330.

Cappelleri, J. a. (2005). The Sexual Health Inventory for Men (SHIM): a 5-year review of research and clinical experience. *International journal of impotence research*, 307--319.

Cappelleri, J. C. (1999). Diagnostic evaluation of the erectile function domain of the International Index of Erectile Function. *Urology*, 346--351.

Carpenter, J. R. (2013). Analysis of longitudinal trials with protocol deviation: a framework for relevant, accessible assumptions, and inference via multiple imputation. *Journal of biopharmaceutical statistics*, 1352--1371.

Dinneen, E. a.-H.-P. (2022). Negative mpMRI rules out extra-prostatic extension in prostate cancer before robot-assisted radical prostatectomy. *Diagnostics*, 1057.

Dinneen, E. a.-M.-H. (2022). NeuroSAFE PROOF: study protocol for a single-blinded, IDEAL stage 3, multi-centre, randomised controlled trial of NeuroSAFE robotic-assisted radical prostatectomy versus standard robotic-assisted radical prostatectomy in men with localized prostate cancer. *Trials*, 584.

6.1 IIEF-5 scoring

The primary outcome for this project is the simplified International Index of Erectile Function (IIEF-5).

The IIEF score, derived from the 15-item International Index of Erectile Function (IIEF), provides a concise evaluation tool for diagnosing erectile dysfunction (ED) and assessing its severity. Rosen selected these five specific items based on their ability to discern the presence or absence of erectile dysfunction, aligning with the NIH definition of the condition (Rosen, 1999). These items primarily centre on erectile function and satisfaction with intercourse.

The questionnaire used-was based the British Association of Urological Surgeons (BAUS) version of the IIEF questionnaire, which varies slightly from the original Rosen wording by allowing for a "0- Did not attempt intercourse" response for questions 2, 4, 5 and 7, as described in the table below:

NEUROSAFE PROOF STUDY QUESTIONNAIRE		ROSEN 1999
Q2	Over the past 3 months when you had erections with sexual stimulation, how often were your erections hard enough for penetration? 0 No sexual activity 1 Almost never or never 2 A few times (less than half the time) 3 Sometimes (about half the time) 4 Most times (more than half the time) 5 Almost always or always	Q2 When you had erections with sexual stimulation, how often were your erections hard enough for penetration? 1 Almost never /never 2 A few times (much less than half the time) 3 Sometimes (about half the time) 4 Most times (much more than half the time) 5 Almost always /always
Q4	Over the past 3 months during sexual intercourse, how often were you able to maintain your erection after you had penetrated (entered) your partner? 0 Did not attempt intercourse 1 Almost never or never 2 A few times (less than half the time) 3 Sometimes (about half the time) 4 Most times (more than half the time) 5 Almost always or always	Q3 During sexual intercourse, how often were you able to maintain your erection after you had penetrated (entered) your partner? 1 Almost never / never 2 A few times (much less than half the time) 3 Sometimes (about half the time) 4 Most times (much more than half the time) 5 Almost always / always
Q5	Over the past 3 months during sexual intercourse, how difficult was it to	Q4 During sexual intercourse, how difficult was it to maintain your erection to completion of intercourse?

	
maintain your erection to completion of intercourse?
 
1 Did not attempt intercourse 2 Very difficult 3 Difficult 4 Slightly difficult 5 Not difficult
	
Q7	
Over the past 3 months when you attempted sexual intercourse, how often was it satisfactory for you?
 
0 Did not attempt intercourse 1 Almost never or never 2 A few times (less than half the time) 3 Sometimes (about half the time) 4 Most times (more than half the time) 5 Almost always or always
	
Q5 When you attempted sexual intercourse, how often was it satisfactory for you?
 
1 Almost never / never 2 A few times (much less than half the time) 3 Sometimes (about half the time) 4 Most times (much more than half the time) 5 Almost always / always

For the item 5, the “Extremely difficult” response was missing, when it should have been offered as a possible answer and scored as 1. And the “Did not attempt intercourse” answer was scored as 1 when it should have been scored as 0.

To improve comparability, we adjusted the response based on the other IIEF-5 responses. For those who answered “1- “Did not attempt intercourse” and had responded “0 Did not attempt intercourse” to all the questions 2, 4 and 7, we assumed the answer would have been 0 (“Did not attempt intercourse”). For all other participants, we left the score as 1 (corresponding to “Extremely difficult”)

The score to the 5 items were then summed, giving an IIEF-5 score ranging from 1 to 25.

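### The item 5 repair also requires a zero on Q2, so some men who report no attempt at intercourse keep one point in the IIEF-5 and IIEF-6

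*SAP*

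**What the plan says.** The primary outcome is the 12-month IIEF-5, the sum of Q2, Q4, Q5, Q7 and Q15 (SAP Section 3.4), compared between arms as a mean difference (Section 4.7). Appendix 6.1 shows the questionnaire as used and discloses two faults in item 5. The hardest grade of difficulty was not offered; the options ran "1 Did not attempt intercourse 2 Very difficult 3 Difficult 4 Slightly difficult 5 Not difficult". And the no-attempt "answer was scored as 1 when it should have been scored as 0".

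Under the repair, a man who ticked 1 on item 5 is rescored to 0 if he also gave the no-attempt zero "to all the questions 2, 4 and 7, we assumed the answer would have been 0". If not, "For all other participants, we left the score as 1", and the SAP reads that 1 as the missing hardest grade.

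The SAP's own table shows that the three zeros do not share one meaning:

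- Q2: "how often were your erections hard enough for penetration? 0 No sexual activity"
- Q4: "how often were you able to maintain your erection after you had penetrated (entered) your partner? 0 Did not attempt intercourse"
- Q7: "0 Did not attempt intercourse 1 Almost never or never"

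Yet the sentence introducing the table describes one common no-attempt "response for questions 2, 4, 5 and 7, as described in the table below". Appendix 6.2 carries the repaired item 5 into the IIEF-6.

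**The concern.** The repair tests for non-attempt with an item that does not measure it. Q2 asks about erections under sexual stimulation. A man may have had stimulation, and answer Q2 with 1 to 5, without attempting intercourse. If he gives the no-attempt answer on Q4, Q5 and Q7 he has said so three times, but Q2 is not zero, the condition fails, and he is scored as though he had attempted intercourse and found it extremely difficult to keep his erection.

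The extra point goes into the primary mean, the IIEF-6, the analysis of men without a bilateral nerve-sparing recommendation (Section 4.10.3) and the imputation model that uses outcomes at each time point (Section 4.11.2). Whether a man receives it depends on Q2, a post-randomisation measure of the function that the intervention is meant to change. Cancellation between arms therefore cannot be taken for granted.

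**Working it through.** **Inputs.** All come from SAP Section 3.4 and Appendix 6.1. Q2, Q4 and Q7 take values 0 to 5; Q5 and Q15 take 1 to 5 as printed. The check assumes that the appendix table reproduces the form as fielded, and uses complete responses only.

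**Step 1: reproduce the stated range.** Under the SAP rule the lowest total has Q2 = Q4 = Q7 = 0, Q5 recoded to 0 and Q15 = 1, which gives 1. The highest is 5 × 5 = 25. This matches the stated range of 1 to 25. The range is the same under the alternative rule below, so it cannot reveal the problem.

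**Step 2: compare two rules over every response pattern.**

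- SAP rule: Q5 goes from 1 to 0 if Q2 = Q4 = Q7 = 0.
- Alternative: Q5 goes from 1 to 0 if Q4 = Q7 = 0, whatever Q2 is.

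They differ only where Q5 = 1, Q4 = Q7 = 0 and Q2 is 1 to 5, with Q15 free: 5 × 5 = 25 patterns. In each, the SAP total is Q2 + 0 + 1 + 0 + Q15 and the alternative total is Q2 + Q15. The difference is always exactly 1.

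- SAP totals run from 1 + 1 + 1 = 3 to 5 + 1 + 5 = 11.
- Alternative totals run from 2 to 10.

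Example: Q2 = 3, Q4 = 0, Q5 = 1, Q7 = 0, Q15 = 2 scores 6 under the SAP rule and 5 under the alternative.

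**Step 3: cut-offs.** The largest affected total is 11, so no pattern crosses ≥15 (SAP Sections 3.6.1 and 3.6.2) or ≥21 (Protocol Section 7.2.1). Among the severity bands in SAP Section 3.6.1, only the boundary between 7 and 8 is touched. It needs Q2 + Q15 = 7, which gives four patterns: (2,5), (3,4), (4,3) and (5,2). The SAP rule scores these 8 (moderate); the alternative scores them 7 (severe).

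**Step 4: how the error responds to function.** Hold Q4 = Q7 = 0, Q5 = 1 as printed, and Q15 fixed. At Q2 = 0 the SAP total is Q15. At Q2 = 1 it is 1 + 1 + Q15. One step on Q2 adds 2 points, of which 1 is artefact.

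**Step 5: effect on the mean difference (unadjusted).**

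Shift = 1 × (affected share, NeuroSAFE − affected share, control)

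The documents give no counts, so these shares are assumptions:

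| NeuroSAFE | Control | Shift (points) |
|---|---|---|
| 10% | 10% | 0 |
| 15% | 10% | +0.05 |
| 25% | 15% | +0.10 |
| 30% | 10% | +0.20 |
| 10% | 20% | −0.10 |

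**The case against.** The strongest defence is that the fault is disclosed, the rule is fixed in advance by statisticians blinded to allocation, and it applies identically to both arms. Because the hardest grade was never offered, some men who ticked 1 may have meant it, and requiring three zeros recodes only unanimous cases. The published five-item form set beside it has no zero on the items shown, so a residual 1 is that form's floor.

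The point about the missing option stands for men with non-zero answers to Q4 and Q7, and the answer is ambiguous where only one of the two is zero. It does not rescue the rule where both are zero: a man who found intercourse extremely difficult would have attempted it. Nor does the published form's floor settle the matter, because the SAP itself says that the no-attempt answer should score 0.

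The objection on size stands in full. If the SD were 5 to 8 (an assumption; the documents give none), 364 evaluable men would give an unadjusted standard error of SD × √(4/364), about 0.52 to 0.84. A shift of 0.10 is then roughly 0.12 to 0.19 of one standard error.

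A reader might infer that the rule favours NeuroSAFE. The documents do not support that. If the intervention moves men from no activity to stimulation without intercourse, it adds men to the affected group and the difference is overstated. If it moves men from there to attempting intercourse, it removes them and the difference is understated. Nothing in the documents says which movement dominates.

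**Conclusion.** The scoring rule misses the SAP's own standard for one coherent group of answers, and it does so in the primary outcome. Appendix 6.1 appears to have carried the no-attempt label over to Q2, where the table shows a different one.

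The size is limited: 1 point per affected man, at IIEF-5 totals of 3 to 11 only. The frequency is unknown, and so are the sign and size of any net shift in the mean difference. A baseline total of 22 to 25, as eligibility requires, cannot be an affected pattern, so baseline adjustment is in practice untouched.

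Two further inferences should be resisted. The recovery proportions and the time-to-recovery curves are not wrong on this account, because no affected total comes near 15 or 21. Nor does it follow that every 1 on item 5 should become 0: where Q4 and Q7 are both non-zero, reading the 1 as the missing hardest grade is reasonable.

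**What to change.** - Recode Q5 from 1 to 0 when Q4 and Q7 were both answered as 0, whatever Q2 is. Leave Q5 at 1 when only one of them is 0.
- Apply the recode before the missing-item step. Section 3.4 sets blank Q4 and Q7 to 0 when at least three items are answered, and the SAP does not say which step comes first. If the recode came second, a man who left both blank would be treated as having denied an attempt twice. Hence the condition must refer to observed zeros.
- Correct the description of the Q2 zero in the Appendix 6.1 text so that it agrees with the table.
- Use the same item 5 score in the IIEF-6, and at every visit where the definitions already apply.
- Report by arm how many men have Q5 = 1, Q4 = Q7 = 0 and Q2 of 1 to 5.

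The cost is one changed condition with an order of operations in the scoring code, a short SAP correction and one small table. Section 2.1 allows limited, justified adjustments of this kind. If unblinding has already occurred, report the primary analysis under both scorings as a sensitivity analysis.

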6.2 IIEF-6 scoring

IIEF-6 was scored similarly to the IIEF-5. It was based on summing the score to the questions 1, 2, 3, 4, 5 and 15 from the IIEF-15. Q2, Q4 and Q5 are shown in the IIEF-6 table below, and Q1 and Q15 are shown below.

Question 5 was scored as described above, before summing all the item, giving a total score between 1 and 30.

NEUROSAFE QUESTIONNAIRE

Q1	Over the past 3 months how often were you able to get an erection during sexual activity? 0 No sexual activity
-----------	-------------------------------------------------------------------------------------------------------------------

- 1 Almost never/never
- 2 A few times (much less than half the time)
- 3 Sometimes (about half the time)
- 4 Most times (much more than half the time)
- 5 Almost always/always

Q15 Over the past 3 months how do you rate your confidence that you could get and keep an erection?

- 1 Very low
- 2 Low
- 3 Moderate
- 4 High
- 5 Very high

6.3 ICIQ scoring

ICIQ	
Q3	How often do you leak urine? 0 never 1 about once a week or less often 2 two or three times a week 3 about once a day 4 several times a day 5 all the time
Q4	We would like to know how much urine you think leaks. How much urine do you usually leak (whether you wear protection or not)? 0 none 2 a small amount 4 a moderate amount 6 a large amount
Q5	Overall, how much does leaking urine interfere with your everyday life? Please ring a number between 0 (not at all) and 10 (a great deal)

6.4 Gleason score and Gleason grade group

The Gleason grade is a pathologist's rating of the most predominant pattern and the second most predominant pattern of a biopsy. A patient's Gleason score can be derived by adding these two Gleason grades together. Gleason scores range from 6 to 10, with 6 being the lowest grade of cancer (Gnanapragasam, 2016). The breakdown of the Gleason grade is shown in the table below:

Grade group	Gleason score
GRADE GROUP 1	Gleason score <= 6
GRADE GROUP 2	Gleason score 7 (3+4)
GRADE GROUP 3	Gleason score 7 (4+3)
GRADE GROUP 4	Gleason score 8 (4+4, 3+5, 5+3)
GRADE GROUP 5	Gleason score 9 – 10 (4+5, 5+4, 5+5)

6.5 Cambridge prognostic groups

Cambridge prognostic groups are specified based on the Grade Group or Gleason score, the Prostate specific antigen (PSA) level and the Tumour stage (the T stage from the TNM staging).

Cambridge Prognostic Group 1 (CPG 1)

- a Gleason score of 6, Grade Group 1.
- and a PSA level less than 10 nanograms per millilitre (ng/ml)
- and a T stage of 1 or 2

Cambridge Prognostic Group 2 (CPG 2)

- [a Gleason score of 3 + 4 = 7, Grade Group 2
- or a PSA level between 10 and 20 ng/ml]
- And
- [a T stage of 1 or 2]

Cambridge Prognostic Group 3 (CPG 3)

- [a Gleason score of 3 + 4 = 7, Grade Group 2
- and a PSA level between 10 and 20 ng/ml
- and a T stage of 1 or 2]
- Or
- [a Gleason score 4 + 3 = 7, Grade Group 3
- and a T stage of 1 or 2]

Cambridge Prognostic Group 4 (CPG 4)

If the patient has **one of the following**:

- a Gleason score of 8, Grade Group 4
- PSA level higher than 20 ng/ml
- T stage of 3

Cambridge Prognostic Group 5 (CPG 5)

[If the patient has **two or more of the following**:

- a Gleason score 8, Grade Group 4
- PSA level higher than 20 ng/ml
- T stage of 3]
- Or
- [a Gleason score 9 to 10, Grade Group 5]
- Or
- [T stage of 4]
